6.1. HOSPITAL STAY

6.1.1. Patient recruitment, blinding and randomization

Subjects will be recruited from the clinical offices of Drs. [name] and [name] during their routine preoperative evaluation for pancreas resection and islet transplantation. During their preoperative evaluation, the purpose of the study and the associated consent form will be explained in detail and the participant will be given time to ask questions. If the subject wishes to participate, the proper consent and HIPAA forms will be signed and dated. The consent form may be signed in person in a clinic or via telehealth using an eConsent/doxy.me. On the doxy.me platform the study participant has the ability to download a copy of the signed consent for their record. They will be informed of this and encouraged to download their copy by the study team member who is obtaining consent. The virtual visit video chat feature of this platform allows for questions from the patient to be answered in real time by the study team. The study team member obtaining consent will also have the ability to review the HIPAA authorization form with the patient and obtain a signature through the doxy.me platform. A copy of the signed consent form will accompany the patient to the operating room for documentation of participation in the study.

Consented patients will be screened based on inclusion and exclusion criteria. If patient meets the criteria, they will be randomized to either AAT or control group by block randomization. The PI ([name]) and the clinical PIs ([name], [name], [name], [name]) of this study will be blinded for the assignment of the study treatment. The Investigational Pharmacy at MUSC will prepare drug infusions using aseptic technique under a sterile hood. In the clinic, a trained RN will infuse the drug and monitor for side effects of AAT. These individuals will not be blinded.

Diabetes care will be managed by the Endocrinology team at MUSC led by [name], co-investigator of our trial. The diabetes care is standardized while in the hospital with insulin drip for all patients post-operatively. The drip is then weaned over the first few days with care individualized by the hospital diabetes management team. The discharge plan is then individualized in accordance with ADA standards.

The required lab tests for the study include an IgA level and the MMTT at time 75 and 365 days. There are no imaging screening tests required for this study. It is noted that many of the safety laboratories will be the same laboratory assessments as are used for the usual surgical care.

One basal serum sample will be collected prior the first infusion of study drug (AAT or normal saline) and be stored for pre-transplant chemokines/cytokines. The basal sample will be obtained before surgery.

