5.2. FORMULATION, DOSING, ADMINISTRATION AND EMERGENCY PRECAUTIONS

Prolastin-C is commercially available, and packed as a lyophilized powder and is ready to use after reconstitution with dilute (sterile water) that comes with the drug. Each pack contains 1000mg of AAT, and 20ml of dilutant. Both Prolastin-C and the dilutant should be stored at temperature not to exceed 25 (77 ° F). Reconstituted product from several vials may be pooled into an empty, sterile IV solution container by using aseptic technique. All the materials will have trial specific labels. The reconstitution should be used within 3 hours. The dosing will be administered at a rate of approximately 0.08ml/kg/min. The 60mg/kg dose takes approximately 15-30 minutes to infuse. If assigned to the placebo group, saline will be infused at the same volume and speed.

Each patient will receive 60mg/kg body weight if assigned in the AAT group. The first dose will be calculated based on the recipient's body weight during admission for transplant. The subsequent doses will be calculated based on the body weight recorded at study entry. The final dose for infusion will be rounded to the nearest whole vial dose, but must be within 10% of calculated dose.

The first infusion of the Investigational Product will start on the day of islet transplantation. Patient will receive 4 weekly doses of AAT or saline 7 ± 3 days apart.

The Investigational Product will be dispensed only by a qualified individual. Vital signs will be recorded within 30 minutes before the infusion, during infusion and 15 minutes after infusion. With each infusion, medical personnel will be available to treat subjects who experience difficulties. Emergency treatment such as 0.3ml to 0.5ml aqueous epinephrine (1:1000 dilution) subcutaneously and other resuscitative measure including oxygen, IV fluids, antihistamines, corticosteroids, vasopressors, and airway management, will be available in the infusion suite.

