5.3. DRUG ACCOUNTABILITY

Under Title 21 of the Code of Federal Regulation (21CFR{312.62 Investigator recordkeeping and record retention.), an investigator is required to maintain adequate records of the drug preparation and disposition, and maintain adequate and accurate case histories that record all observations and other data pertinent to the investigation.

Records for receipt, storage, use and disposition will be maintained by the unblinded study coordinator. A drug dispensement log including the identification of each subject, date and quantity of drug used will be kept current for each subject. Any drug accidentally or deliberately destroyed will be recorded as well.

5.4. CRITERIA FOR SCHEDULE ADJUSTMENT, DOSE-MODIFICATION, DISCONTINUATION OF INVESTIGATIONAL DRUG.

5.4.1. No schedule adjustment and/or dose modification is foreseen, except for discontinuation of drug as detailed below:

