5.4.2. Criteria for discontinuation of Investigational Product

Any subject may voluntarily withdraw (ie, reduce the degree of participation in the study) consent for continued participation and data collection. The reason for withdrawal will be recorded on the appropriate CRF. Patients who discontinue the treatment with the investigational drug will not be withdrawn from the study by default, but will complete observations as per the protocol, unless otherwise they withdraw their consent.

Discontinuation (ie, complete withdrawal from study participation) may be due to dropout (ie, active discontinuation by subject) or loss to follow-up (ie, discontinuation by subject without notice or action), or death. Additionally, the investigator and sponsor have the discretion to discontinue any subject from the study if, in their judgment, continued participation would pose an unacceptable risk for the subject. Subjects meeting the definition for intent-to-treat who are prematurely terminated from study treatment will not be replaced.

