8.2.1. MODIFIED INTENT-TO-TREAT POPULATION

The modified intent-to-treat (mITT) population includes all randomized subjects who meet study eligibility criteria and have received at least one injection (of AAT or placebo). The primary efficacy measures will be analyzed with the mITT population.

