8.7. ASSESSMENT TIME WINDOWS

The Baseline visit should occur within 28 days of the screening visit. For all scheduled visits, allowable visit windows and study procedures are \pm 14 days from the calculated target day. The target day is defined as (Baseline Visit + 75 days) for the Day 75 target day, and (Baseline Visit + 365 days) for the Day 365 target day. If multiple measurements occur within the assessment time window, the measurement closest to the scheduled target day will be analyzed. Data collected outside of the specified time window will not be included in the primary analysis.

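### Randomisation is not tied to admission or confirmed surgery, so a patient whose operation is cancelled before the first infusion can use a 2:1 allocation and then fall outside the primary analysis set

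*Combined protocol and SAP*

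**What the plan says.** **Order of events.** Section 6.1.1 recruits patients "during their routine preoperative evaluation for pancreas resection and islet transplantation", in clinic or by telehealth. Consent comes first, then screening against the criteria, then: "If patient meets the criteria, they will be randomized to either AAT or control group by block randomization". Section 4 also places randomisation after consent, and 4.3 has an eligible, randomised patient receive a study number. Section 4.1 requires only that surgery is scheduled.

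**Interval before treatment.** Section 8.7: "The Baseline visit should occur within 28 days of the screening visit". Appendix 1 checks inclusion and exclusion at Screening only and has no randomisation row.

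**When the first infusion can be prepared.** Section 5.2 bases the first dose on "body weight during admission for transplant" and adds: "The reconstitution should be used within 3 hours". Section 6.1.2 gives it on the day of transplant, before anesthesia.

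**Who is analysed.** The mITT set in 8.2.1, which is primary for efficacy, takes randomised, eligible patients who "have received at least one injection (of AAT or placebo"). Section 4.3 calls a randomised patient evaluable under intention to treat, as the statistical plan defines it. Section 5.4.2 states: "Subjects meeting the definition for intent-to-treat who are prematurely terminated from study treatment will not be replaced". Section 8.2 defines mITT, per-protocol and safety sets, but no plain intention-to-treat set.

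**What the target counts.** Section 4 sets a goal of 48 patients, each randomised. Sections 3.1 and 8.3 describe 32 and 16 patients who receive AAT or control treatment. The 10% allowance in 8.3 is for loss to follow-up over the 12 months. Section 8.8 lists the proportion of enrolled patients successfully transplanted as a feasibility measure.

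**The concern.** Major elective surgery can be cancelled or postponed, and a patient can withdraw or become ineligible between the clinic visit and the operation. If the allocation has already been drawn, such a patient takes up a place in a block of 3 or 6 and contributes nothing to the primary analysis. With 16 placebo allocations, each one lost matters, both for the comparison and for the means, SDs and effect sizes that 8.3 names as the trial's most important product.

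The documents also leave three things open for this patient: whether he or she is replaced, whether he or she counts towards the 48, and whether the intention-to-treat wording in 4.3 and 5.4.2 means the mITT set or a set that the plan never defines.

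The exposure buys nothing that the plan mentions. The pharmacy cannot calculate the first dose before admission, must use the product soon after reconstitution, and needs no allocation weeks ahead.

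**Working it through.** **Inputs from section 8.3:** 32 AAT and 16 placebo patients; difference 0.9 SD; 80% power; 10% loss to follow-up. **Assumed:** two-sided alpha 0.05 (8.3 states none; 8.11 uses 95% intervals); equal SDs in both arms; the same pre-dose loss c in each arm. The documents give no pre-dose loss rate, so c = 5, 10 and 15% is shown as a range. The calculation takes 48 to be the number randomised.

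**Formula.** n(AAT) = 32 × (1 − c) × 0.9 and n(placebo) = 16 × (1 − c) × 0.9. SE = √(1/n(AAT) + 1/n(placebo)) in SD units. Power (normal approximation) = Φ(0.9/SE − 1.96).

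**Step 1: reproduce the plan (c = 0).** n = 28.8 and 14.4; SE = √(1/28.8 + 1/14.4) = 0.3227; 0.9/0.3227 = 2.789; Φ(0.829) = 79.6%. This matches the stated 80%. A noncentral t test with the same numbers gives 77.7%. The stated power therefore uses all 48 allocations and has no slack for loss before the first infusion.

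**Step 2: add pre-dose loss.**

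| Never dosed (assumed) | mITT, 48 × (1 − c) | Evaluable after 10% loss | SE | Power, normal | Power, t test | Difference detectable with 80% power, (1.96 + 0.842) × SE |
|---|---|---|---|---|---|---|
| 0% | 48 | 43.2 | 0.3227 | 79.6% | 77.7% | 0.90 SD |
| 5% | 45.6 | 41.0 | 0.3311 | 77.6% | 75.5% | 0.93 SD |
| 10% | 43.2 | 38.9 | 0.3402 | 75.3% | 73.1% | 0.95 SD |
| 15% | 40.8 | 36.7 | 0.3501 | 72.9% | 70.5% | 0.98 SD |

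Each 5% lost costs about 2 to 2.4 points.

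**Step 3: placebo arm.** If each of the 16 placebo patients has a 10% chance of never being dosed, the binomial probability that two or more are lost (14 or fewer dosed) is 49%; for three or more it is 21%. The planned 2:1 ratio is then not assured in the mITT set.

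**Step 4: compensating by enrolment.** To dose 48 under early randomisation, 48/(1 − c) must be randomised: 51, 54 or 57 patients at 5, 10 or 15%.

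**The case against.** **The timing is inferred.** No sentence dates randomisation, 6.1.1 sits under a heading about the hospital stay, and a site could randomise at admission without breaching the text. This stands as a limit. A reader might infer that the protocol fixes randomisation at the screening visit; it does not. But consent, screening and randomisation are described in sequence from the preoperative evaluation onwards, sections 4 and 4.3 agree with that sequence, and nothing delays the last step.

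**32 and 16 may already be treated patients.** Sections 3.1 and 8.3 read that way, and if they govern, the power loss disappears. Section 4 counts randomised patients. The documents support neither reading alone, so the figures above are conditional.

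**Replacement is not clearly barred.** A reader might infer that 5.4.2 forbids replacing a never-dosed patient. Its sentence concerns patients terminated from treatment who meet an intention-to-treat definition. The only related definition in 8.2 requires an injection, so never-dosed patients may lie outside the rule. The text is unclear rather than prohibitive.

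**No bias is shown.** A reader might infer that unblinded staff hold allocations for weeks and could affect who proceeds to surgery. Section 5.3 says only that drug records "will be maintained by the unblinded study coordinator"; it does not show that anyone learns an allocation early. Section 8.5 blinds patients, treating investigators and endpoint assessors, and keeps the treatment codes in sealed envelopes. Nothing says that the unblinded staff decide on surgery, and 28 days is a maximum interval.

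**The stakes are moderate.** Section 8.3 declares all hypothesis testing exploratory, and 8.8 already reports how many enrolled patients are transplanted. Both points stand. They lower the weight of the power figures but do not settle how a never-dosed patient is counted.

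**Conclusion.** The point holds as a cheap design improvement. On the plain sequence in 6.1.1, a patient whose surgery is cancelled before the first infusion uses an allocation and is excluded from the mITT set, and the plan does not clearly say whether that patient is replaced or counted in the 48. The harm is to precision and allocation balance. If 48 counts randomised patients, pre-dose losses of 5 to 15% would lower power by about 2 to 7 points: from 79.6% to between 77.6% and 72.9% by the normal approximation, or from 77.7% to between 75.5% and 70.5% by t test. The loss rates are assumptions, and the size of the effect depends on them. The documents do not support the stronger conclusions that randomisation is dated to screening, that replacement is forbidden, or that the comparison is biased.

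**What to change.** Leave consent and screening where they are, and make these changes:

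1. **6.1.1, 4 and 4.3:** randomise at admission for TP-IAT, after re-confirming eligibility. The unblinded coordinator or the investigational pharmacy draws the next allocation when the admission weight is received.
2. **4, 3.1 and 8.3:** state that the 48 (32 and 16) are patients randomised at that point.
3. **Appendix 1:** add a randomisation row and the eligibility re-check.
4. **8.5:** align the description of who holds and opens the treatment codes.
5. **4.3 and 5.4.2:** align the intention-to-treat wording with the mITT definition in 8.2.1, and say whether a randomised, never-dosed patient is replaced.
6. **Reporting:** list any randomised, never-dosed patients by arm, with reasons.

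The cost is text edits in several sections and a pharmacy or coordinator instruction; no visits, staff or patients are added. The downside is that the allocation must be drawn at admission or on the morning of surgery. The change does not help where surgery is abandoned after the first infusion: that patient stays in the mITT set but may have no islet count with which to normalise the primary endpoint.

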3.5.3. Exploratory endpoints

- Measurements of primary and secondary endpoints at day 75±14.
- Time course of instant blood mediated inflammatory reaction as measured by thrombin-anti-thrombin (TAT), C5a and c-peptide levels before, in the middle and after initiation of islet infusion, and 3h post islet infusion.
- Time course of inflammatory chemokines/cytokines as assessed by serum level of CXCL8, CCL2 (MCP-1), CCL3, CCL4, CXCL10 (IP-10), CXCL9 (MIG), IL-6, IL-10, INF- γ , TNF- α , and IL-1 β [pre-infusion, and 24, 72 and 168hrs, and day 14, and 21 after the end of islet infusion].
- Basal to 240 min time course of glucose, and C-peptide derived from the MMTT (day 75±14 to day 365±14).
- The proportion of patients with an HbA1c \leq 6.5% (day 365±14 days post-transplant only)
- Cumulative number of severe hypoglycemia events.
- The proportion of patients with an HbA1c \leq 6.5% at day 365±14 AND are free of severe hypoglycemic events from day 75±14 to day 365±14 inclusive.
- Daily oral Morphine Equivalents on day prior to visit (day 75±14 to day 365±14).
- Proportion of patients remaining on narcotics (day 75±14 to day 365±14).
- RNA expression profile in peripheral blood mononuclear cells (PBMCs) at 168 h post transplantation. RNA analysis will be done in at least 10 patients to guarantee post-treatment sampling in at least 3-4 patients randomized to AAT and 3-4 to control.
- SF-12 Quality of Life score

3.5.4. Safety endpoints:

- Incidence and severity of Adverse Events and Serious Adverse Events
- Standard laboratory tests including hematology (hematocrit, hemoglobin, red blood cells, platelets, white blood cells, differential white blood cell count), clinical chemistry (sodium, potassium, serum creatinine, blood urea nitrogen, total bilirubin, alanine aminotransferase (ALT), aspartate aminotransferase (AST) and coagulation (International Normalized Ratio (INR), partial thromboplastin time (PTT)), at pre-transplant hospital admission and post-transplant hospital

discharge].

- Vital signs, i.e. blood pressure (BP) and heart rate (HR) at pre-transplant hospital admission and post-transplant hospital discharge. ALT/AST, INR/PTT
- Weight loss from pre-transplant value [time frame: day 75±14 and 365±14 after the transplant]
- Serum level of albumin and pre-albumin (absolute and change from pre-transplant value) [time frame: day 75±14 and 365±14 after the transplant].

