6.1.2 Infusion of the Investigational Product

Infusion of AAT will start on the day of islet transplantation before anesthesia and pancreatectomy, which is approximately 6-8 hours before islet infusion. The clinical PIs, Drs. [name] and [name], will identify the time to start the study drug infusion. Starting and ending time of drug administration, amount of drug infused, and infusion rate will be recorded for each subject. On Average, TP-IAT patients stay in the hospital for 7-28 days after islet transplantation. If they stay till 21 days post transplantation, they can have all four AAT injections in the hospital. If they are discharged earlier, patients will be requested to return to MUSC for additional drug infusion(s). A nurse will administer the AAT or placebo infusion to the patient while in the hospital. A nurse in the GI surgery clinic or SCTR outpatient clinic will administer AAT or placebo to patients discharged but returning for one of the weekly visits. The nurses infusing these drugs will be trained on the day of administration concerning the few known side effects of AAT and rate of infusion.

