8.5. BLINDING

The study will be conducted in a double blind manner. Identical study treatment infusion packages will be prepared by our clinical trial coordinator. Study subjects, treating investigators, and efficacy endpoint assessors will be blinded to treatment assignments.

The clinical trial coordinator will produce identical sealed envelopes that contain identification of treatment codes. Prior to initiation of the trial, these envelopes will be stored in a locked file cabinet at the coordinator's office in its limited access central file room.

The DSMB will be partially unblinded for the closed reports (data reported by treatment groups "A" and "B" only). However, if it so wishes, it may be completely unblinded at any time during the trial. If the DSMB wishes to be unblinded on a particular subject only, the NIDDK Liaison to the DSMB should email the request to the unblinded biostatistician.

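### The clinic nurse who infuses the product and watches for side effects is unblinded, and the inpatient nurse's status is not stated, so recording of infusion-time symptoms is open to observer bias

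*Combined protocol and SAP*

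**What the plan says.** On the nurse's role, section 6.1.1 states: "In the clinic, a trained RN will infuse the drug and monitor for side effects of AAT. These individuals will not be blinded". The phrase about these individuals may also take in the pharmacy staff of the preceding sentence, but on any reading it includes the nurse. Section 6.1.2 covers both settings: one nurse infuses during the hospital stay and another at return visits to an outpatient clinic. It adds that infusing nurses "will be trained on the day of administration concerning the few known side effects of AAT". It does not say whether the hospital nurse is blinded.

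On blinding, section 8.5 states: "The study will be conducted in a double blind manner". It continues: "Identical study treatment infusion packages will be prepared by our clinical trial coordinator". The roles it protects are listed in one sentence: "Study subjects, treating investigators, and efficacy endpoint assessors will be blinded to treatment assignments". Sealed envelopes hold the treatment codes.

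On safety data, section 5.2 requires observation around every dose: "Vital signs will be recorded within 30 minutes before the infusion, during infusion and 15 minutes after infusion". It does not say who records. Section 3.5.4 makes this a safety endpoint: "Incidence and severity of Adverse Events and Serious Adverse Events". Section 8.10 analyses safety mainly as per-subject yes/no indicators by logistic regression, with Cox models to compare arms where time to event suits better.

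**The concern.** In the clinic, one person gives the product, is not blinded, has been briefed on the active drug's side effects, and has the task of looking for them. The drug-related reactions that section 2.3.2 takes from the package insert are chills, malaise, headache, rash, hot flush and pruritus. Several are subjective or brief, and in patients recovering from major abdominal surgery it takes judgement to decide whether mild malaise or a chill is worth noting. Knowing the arm can sway that judgement.

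Comparing safety is part of the stated objective (section 3.4), and section 8.3 says the trial's main value is to supply estimates for a larger trial. An arm difference produced or hidden by unequal recording would carry into that design. The plan also appears to have most of what is needed to blind the nurse, so the exposure looks avoidable.

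**Working it through.** The plan has no figure to reproduce here. The check sets the sections side by side.

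1. **Who is unblinded.** Section 6.1.1: the clinic nurse, explicitly. Section 6.1.2: hospital nurse, status not given. Dose 1 is always given in hospital, before anesthesia. The doses on days 7, 14 and 21 may fall before or after discharge, since section 6.1.2 puts the stay at 7 to 28 days. The explicit statement therefore covers the later doses of patients already discharged, and the remaining doses are undefined.

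2. **Who is blinded.** Section 8.5: subjects, treating investigators and efficacy assessors. Section 6.1.1 adds the principal investigator and the clinical principal investigators. Neither section names a safety observer at infusion.

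3. **Is there a stated need for the nurse to know?** None was found. Infusions are prepared away from the bedside (6.1.1), saline runs at the same volume and speed as the active product (5.2), packages are identical and sealed codes exist (8.5). The emergency provisions in section 5.2 apply to every infusion regardless of arm.

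4. **What else captures these events?** Section 7.1.1 has the investigator actively question the subject and judge severity and relationship. Section 8.10 has subjects report any new symptom at any time, whatever they attribute it to. Appendix 1 schedules adverse-event recording on the infusion days without saying who does it. No section requires a blinded observer at infusion or a symptom checklist common to both arms.

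5. **How far do those routes protect the comparison?** Let the true symptom proportion p be equal in both arms. Let n_A and n_P be the nurse's chance of noting a symptom on AAT and placebo, and s the chance that it is captured through the subject or investigator. Assume the routes are independent and s is equal in both arms. The observed proportion in an arm is p × [1 − (1 − s)(1 − n)], so the observed ratio is [1 − (1 − s)(1 − n_A)] / [1 − (1 − s)(1 − n_P)]. It equals 1 only if n_A = n_P or s = 1. A high s pulls it towards 1. The documents give none of these quantities, so the ratio cannot be evaluated.

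6. **How sensitive are the rates to one record?** Full trial: 1/32 = 3.1 percentage points on AAT and 1/16 = 6.25 on placebo. Initial block, which section 8.4 intends for early safety assessment: 1/4 = 25 points and 1/2 = 50 points. These figures show how coarse the rates are. They do not estimate bias.

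7. **Who prepares the infusions?** Section 6.1.1 says the Investigational Pharmacy; section 8.5 says the clinical trial coordinator; section 5.3 has an unblinded study coordinator keep the drug records. These need to be reconciled before the list of unblinded roles can be closed.

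**The case against.** The strongest reply is that unblinding the pharmacy and clinic infusion staff is openly disclosed, and that the people whose judgement matters most are blinded. Most of the listed reactions are felt by the subject, who is blinded and asked to report everything. The blinded investigator asks actively and does not depend on the nurse's notes, and no section makes the nurse the sole recorder. All of this stands, and it is why the concern is limited to transient symptoms that may go unmentioned later.

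Several stronger readings do not stand:
- A reader might infer that the nurse at every infusion knows the arm. The sentence is about the clinic, and the inpatient status is unstated. Nor does the text say how the clinic nurse learns the allocation.
- A reader might infer that nobody blinded detects infusion events. Sections 7.1.1 and 8.10 contradict that.
- A reader might call infusion reactions the expected harm. Section 7.2 says no events are expected from either infusion. Section 2.3.2 gives drug-related rates of 3.2% for chills and 1.6% for each other symptom. At 3.2%, about one of 32 AAT patients would be affected (0.032 × 32 = 1.02), although all-cause symptoms after surgery could be commoner.
- A reader might attach a relative risk to the bias. That would need recording rates by arm, which the documents do not supply.
- A reader might argue that nurses would cue patients and so distort quality of life or narcotic use. Nothing suggests disclosure, and those outcomes are taken at days 75 and 365, long after the last dose on day 21.

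It is also fair to say that identical packages need not mean indistinguishable contents: one arm is a reconstituted plasma protein, the other saline. The remedy has to allow for that.

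**Conclusion.** The point holds in a limited form. The plan leaves the clinic infusion nurse unblinded without a reason, does not state the inpatient nurse's position, and lists no blinded safety observer at infusion in a trial it calls double blind. Detection and recording of transient infusion-time symptoms are therefore open to observer bias, in a direction and of a size that the documents do not allow to be calculated. Blinded self-report and investigator questioning reduce it but cannot be assumed to capture everything. The primary endpoint, a laboratory C-peptide measure at day 365, is not directly affected, and section 8.3 already treats all hypothesis testing as exploratory. The conclusion assumes that the nurse's observations contribute to the adverse-event record, which the monitoring role implies but the text does not spell out. This is an inexpensive improvement to the safety comparison and does not threaten the trial's main result.

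**What to change.** Change sections 6.1.1, 6.1.2 and 8.5 together so that only the pharmacy or other preparer and the code holder are unblinded. Infusing nurses, in hospital and in clinic, receive the identical package labelled by subject number only, with an opaque cover if the contents can be told apart and the sealed code available for emergencies. Section 8.5 should list every unblinded role, and sections 5.3, 6.1.1 and 8.5 should agree on who prepares the infusions. If the contents cannot be masked, say so as the reason for the nurse being unblinded, and use the same infusion-symptom checklist in both arms.

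The cost is protocol wording and minor labelling or cover work, with no extra staff or visits. The downside is that emergency unblinding goes through the sealed code instead of being known at the bedside.
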